9.2.2.3 Reporting Serious Adverse Events After the Protocol-required Reporting Period

There is no requirement to monitor study subjects for serious adverse events following the protocol-required reporting period or after end of study. However, these serious adverse events can be reported to Amgen. In some countries (eg, European Union [EU]

member states), investigators are required to report serious adverse events that they become aware of after end of study. If serious adverse events are reported, the investigator is to report them to Amgen within 24 hours following the investigator's knowledge of the event.

Serious adverse events reported outside of the protocol-required reporting period will be captured within the safety database as clinical trial cases for the purposes of expedited reporting.

9.2.2.4 Reporting a Safety Endpoint as a Study Endpoint

Safety endpoints (eg, treatment emergent adverse events) that are study endpoints are reported on an Event CRF.

9.3 Pregnancy and Lactation Reporting

If a female subject becomes pregnant, or a male subject fathers a child, while the subject is taking evolocumab, report the pregnancy to Amgen Global Patient Safety as specified below.

In addition to reporting any pregnancies occurring during the study, investigators should monitor for pregnancies that occur after the last dose of protocol-required therapies and for an additional 15 weeks after the end of treatment with investigational product, report the pregnancy to Amgen as specified below.

The pregnancy should be reported to Amgen Global Patient Safety within 24 hours of the investigator's knowledge of the event of a pregnancy. Report a pregnancy on the Pregnancy Notification Worksheet ([Appendix C](#)). Amgen Global Patient Safety will follow-up with the investigator regarding additional information that may be requested.

If a female subject becomes pregnant during the study, the investigator should attempt to obtain information regarding the birth outcome and health of the infant. If a male subject's female partner becomes pregnant, the investigator should discuss obtaining information regarding the birth outcome and health of the infant from the pregnant partner.

If the outcome of the pregnancy meets a criterion for immediate classification as a Serious Adverse Event (eg, female subject experiences a spontaneous abortion, stillbirth, or neonatal death or there is a fetal or neonatal congenital anomaly) the investigator will report the event as a Serious Adverse Event.

If a female breastfeeds while taking protocol-required therapies report the lactation case to Amgen as specified below.

In addition to reporting a lactation case during the study, investigators should report lactation cases that occur 15 weeks after the last dose of protocol-required therapies.

Any lactation case should be reported to Amgen Global Patient Safety within 24 hours of the investigator's knowledge of event. Report a lactation case on the Lactation Notification Worksheet ([Appendix C](#)). Amgen Global Patient Safety will follow-up with the investigator regarding additional information that may be requested.

10. STATISTICAL CONSIDERATIONS

10.1 Study Endpoints, Analysis Sets, and Covariates

10.1.1 Study Endpoints

10.1.1.1 Co-Primary Endpoints

- Mean percent change from baseline in LDL-C at weeks 10 and 12
- Percent change from baseline in LDL-C at week 12

10.1.1.2 Secondary Endpoints

- The mean of weeks 10 and 12 and for week 12 for the following:

Tier 1:

- Change from baseline in LDL-C
- Percent change from baseline in non-HDL-C
- Percent change from baseline in ApoB
- Percent change from baseline in total cholesterol
- Achievement of target LDL-C < 70 mg/dL (1.8 mmol/L)
- LDL-C response (50% reduction of LDL-C from baseline)

Tier 2:

- Percent change from baseline in Lp(a)
- Percent change from baseline in triglycerides
- Percent change from baseline in HDL-C
- Percent change from baseline in VLDL-C

10.1.1.3 Safety Endpoints

- Subject incidence of treatment emergent adverse events
- Safety laboratory values and vital signs at each scheduled assessment
- Incidence of anti-evolocumab antibody (binding and neutralizing) formation

10.1.1.4 Exploratory Endpoint(s)

- Mean percent change from baseline in ApoA1 at weeks 10 and 12
- Percent change from baseline in ApoA1 at week 12
- Change from baseline in hsCRP
- PCSK9 change from baseline at each scheduled assessment
- Change and percent change from baseline at each scheduled assessment in each of the following parameters:
 - LDL-C
 - total cholesterol
 - non-HDL-C
 - ApoB
 - VLDL-C
 - HDL-C
 - ApoA1
 - triglycerides
 - Lp(a)

10.1.2 Analysis Sets

The full analysis set (FAS) includes all randomized subjects who received at least 1 dose of investigational product. This analysis set will be used in both efficacy and safety analyses. In efficacy analyses, subjects will be grouped according to their randomized treatment group assignment. For safety analyses, subjects will be grouped according to their randomized treatment group assignment with the following exception: if a subject receives treatment throughout the study that is different than the randomized treatment group assignment, then the subject will be grouped by the actual treatment group.

The completer analysis set (CAS) includes subjects in the FAS who adhered to the scheduled investigational product regimen and have observed values for the co-primary endpoints.

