6.2.1.1 Dosage, Administration, and Schedule

Investigational product will be administered SC (evolocumab or matched placebo) at the investigator site by a qualified staff member in accordance with instructions in the IPIM. Investigational product administration by SC injection at each visit must be done after vital signs, electrocardiogram (ECG), and blood draw procedures, if applicable. The date, time, and amount of evolocumab or placebo will be recorded on the individual subject's worksheet and/or electronic case report form (eCRF). The box number of investigational product (active drug or placebo) is to be recorded on each subject's Drug Administration electronic case report form (eCRF).

After investigational product administration at each dosing visit, subjects should be observed for at least 30 minutes before being discharged.

Approved

In the Q2W regimen, 140 mg of AMG 145 will be administered subcutaneously every 2 weeks via one 1.0 mL prefilled AI/pen.

In the QM regimen, 420 mg of evolocumab will be administered subcutaneously once a month via three 1.0 mL prefilled AI/pens. The prefilled AI/pens injections should be administered in a consecutive fashion with all injections completed within 30 minutes.

Details of preparing and administering investigational product are included in the IPIM provided by Amgen at the start of the study. The dosing schedule is described by a [schema](#) in the protocol synopsis.

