h: Including assessment/review for adverse events/serious adverse events/disease related events/adverse device effects. Only AEs/ADEs possibly related to study procedures and serious adverse events are collected during the screening period

i: During the treatment period, in addition to the in-clinic administration at D1, W8 and W10 (as applicable), subjects randomized to QM are expected to administer non-clinic IP at W4 and subjects randomized to Q2W IP are expected to administer non-clinic IP at W2,W4, and W6.

j: Only for subjects randomized to Q2W IP

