## **5.3 Other Study Related Definitions**

### Actual Treatment Group

A subject's actual treatment group is the randomized treatment group, unless the subject receives treatment throughout the study that is different than the randomized treatment group assignment, in which case the actual treatment group is the treatment received.

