### 6.2 Safety Analysis Set

Safety Analysis Set is same as the Full Analysis Set. For safety analyses, subjects will be grouped according to their actual treatment group (as defined in [Section 5.3](#)).

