## 9. Statistical Methods of Analysis

### 9.1 General Considerations

The efficacy and safety analyses will be performed on the FAS. Unless specified otherwise, the FAS will be the default analysis set in this study and data will be summarized by randomized treatment group **using the analysis window specified in Table 12-1**. Analyses will be performed separately by each dose frequency (Q2W and QM) unless specified otherwise.

[figure not shown]
Subject disposition, demographics, baseline characteristics and exposure to IP will be summarized by treatment group. Summary statistics for continuous variables will include the number of subjects, mean, median, SD or standard error, minimum, and maximum. For categorical variables, the frequency and percentage will be given.

Methods of handling missing data for efficacy endpoints will be described below. Missing data will not be imputed for safety endpoints.

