## **9.6 Safety Analyses**

### **9.6.1 Adverse Events**

The Medical Dictionary for Regulatory Activities (MedDRA) version 22.0 or later will be used to code all events categorized as adverse events (AEs) to a system organ class and a preferred term. Severity of AEs will be graded using the CTCAE and recorded on the eCRF. All treatment-emergent adverse event tables will be summarized by actual treatment group. Treatment-emergent adverse events are events with an onset after the administration of the first dose of IP as defined in [Section 5.3](#).

Subject incidence of all treatment-emergent AEs, serious AEs, AEs leading to withdrawal of investigational product, and fatal AEs will be tabulated by system organ class, high level term, and preferred term in descending order of frequency.

Summaries of treatment-emergent and serious AEs occurring in at least 1% of the subjects by preferred term in any treatment arm will be provided in descending order of frequency.

**All the summary of treatment-emergent adverse event/serious adverse event mentioned above will also include those reported as Disease Related Events (DRE).** Subject incidence of DREs will be summarized **separately** by system organ class and preferred term for all treatment-emergent DREs and fatal DREs **as well**.

Subject incidence of treatment-emergent adverse events related to a device will be tabulated by preferred term in descending order of frequency by treatment group.

Subject incidence of treatment-emergent adverse events associated with injectable protein therapies will be summarized by category and preferred term:

- Injection site reactions
- Hypersensitivity or allergic reactions

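### For safety, a placebo subject who received evolocumab at some or most doses, but not throughout, is still counted as placebo

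*Protocol*

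**What the plan says.** The protocol's default for safety is the randomized arm: "For safety analyses, subjects will be grouped according to their randomized treatment group assignment with the following exception". The one exception, in Protocol 10.1.2 and again in the synopsis, applies "if a subject receives treatment throughout the study that is different than the randomized treatment group assignment".

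The SAP uses a different label for the same rule. SAP 6.2 states: "For safety analyses, subjects will be grouped according to their actual treatment group". SAP 9.6.1 adds: "All treatment-emergent adverse event tables will be summarized by actual treatment group". But SAP 5.3 makes the actual treatment group equal to the randomized group "unless the subject receives treatment throughout the study that is different than the randomized treatment group assignment".

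The laboratory and antibody sections (SAP 9.6.2 and 9.6.4) have no grouping rule of their own. They fall under SAP 6.2 or under the general default in SAP 9.1, by which "data will be summarized by randomized treatment group".

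Neither document has a rule for a subject who received both products, and neither plans a listing of such subjects.

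**The concern.** Product is given on several occasions, so an error can affect some doses and not others. The exception covers only a subject who was wrong on every occasion. A subject randomized to placebo who received evolocumab at one dose, or at nearly all of them, is reported as unexposed. A reaction or an antibody that follows real exposure then appears in the placebo column.

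Antibodies are where this would be most visible. Protocol 7.3 drops follow-up of a subject positive for neutralizing antibodies only once it is established that the subject received no evolocumab. The test there is any exposure. The incidence table uses exposure throughout. The same subject could be followed as exposed and tabulated as placebo.

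At stake is the attribution of a few events, or one, in safety tables whose placebo arms are small. The efficacy analyses are by randomized group and are not affected.

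**Working it through.** The plan states no figure on this point, so there is none to reproduce. The check is a reading of the rules, followed by simple proportions.

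**Dose counts (Protocol 7.1, Table 2 and its footnotes).** In-clinic doses are at Day 1 and Week 8, plus Week 10 for Q2W. For home doses, "subjects randomized to Q2W IP are expected to administer non-clinic IP at W2,W4, and W6"; QM subjects have one, at Week 4.
- Q2W: Day 1 and Weeks 2, 4, 6, 8, 10 = 6 doses
- QM: Day 1 and Weeks 4, 8 = 3 doses

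**Most wrong doses that still fall short of throughout.** Q2W: 5 of 6 = 83%. QM: 2 of 3 = 67%.

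**Grouping of such a placebo subject.**
- Protocol 10.1.2: the exception is not met, so placebo.
- SAP 5.3 and 6.2: the actual group equals the randomized group, so placebo.
- SAP 9.1 default, if it governed instead: randomized group, so placebo.

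All routes agree.

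**Expected effect.** Let p0 be the event risk on placebo, p1 the risk on evolocumab, and k the number of partly exposed subjects left in a placebo arm of 75 (planned size, Protocol 10.2). Assume partial exposure carries the full risk p1. Then

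expected placebo rate = [(75 − k)·p0 + k·p1]/75 = p0 + k·(p1 − p0)/75.

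The documents give no risk difference. Taking 5 to 10 percentage points as an assumption and k = 1:
- 5/75 = 0.07 points
- 10/75 = 0.13 points

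If partial exposure carries less than the full risk, the shift is smaller. The expected evolocumab rate stays at p1, because leaving out a subject with the same risk as the rest of that arm does not change its expectation.

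**Ceiling.** If the mis-assigned subject has the event and no other placebo subject does, the placebo arm shows 1/75 = 1.33% in place of 0/74.

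**Extreme illustration.** Every mis-assigned subject has the event (for example, is antibody-positive) and nobody else in either arm does. Arms are 75 and 150 as planned.

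| k | Placebo, present rule | Evolocumab, present rule | Placebo, any-dose rule | Evolocumab, any-dose rule |
|---|---|---|---|---|
| 1 | 1/75 = 1.33% | 0/150 | 0/74 | 1/151 = 0.66% |
| 2 | 2/75 = 2.67% | 0/150 | 0/73 | 2/152 = 1.32% |
| 3 | 3/75 = 4.00% | 0/150 | 0/72 | 3/153 = 1.96% |

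The values of k are assumptions, since no mis-dosing rate is given. Actual denominators may also differ from the planned ones, because SAP 3.2 and 6.1 remove some enrolled subjects from all analyses.

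**The case against.** The strongest reply is that the rule is explicit, prespecified and the same in both documents, and that grouping by randomized arm unless the treatment was wrong throughout is one convention among several. Consistency is conceded. But the rule still places exposed subjects in the unexposed column, which is a matter of substance in a safety table.

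Several stronger readings are tempting, and the documents do not support them.

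- **That each such subject moves the placebo rate by 1.3 points.** That is the ceiling. On the assumed risk differences above, the expected shift is about 10 to 20 times smaller.
- **That the rule also lowers the evolocumab rate and always narrows the contrast.** The evolocumab rate is understated only when the subject has the event. If the subject has none, keeping them in placebo slightly lowers the placebo rate. The upward bias holds on expectation, and only for events that evolocumab increases. The rule also works in reverse: an evolocumab subject given some placebo stays in evolocumab.
- **That one box error on Day 1 is the likely route.** Table 2 shows home product dispensed on Day 1, so an error confined to that supply could reach up to 4 of 6 Q2W doses or 2 of 3 QM doses. The documents do not say how many pens a box holds or how many box assignments a subject receives. An assignment error affecting every dose, which the exception does cover, cannot be ruled less likely.
- **That mis-dosing happened.** Nothing says so. Boxes are assigned through IVRS/IWRS (Protocol 12.2), which should make it rare.
- **That an antibody-positive placebo subject would simply pass as assay background.** Box numbers, PCSK9 and LDL-C would let the team check real exposure. That helps interpretation of the individual case, but the table stays as it is.

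**Conclusion.** The point holds as a defect in the grouping rule, with a small and possibly nil effect. Literally applied, Protocol 10.1.2 and SAP 5.3 and 6.2 count a placebo subject with up to 5 of 6 Q2W or 2 of 3 QM evolocumab doses as placebo in the adverse event, laboratory and antibody tables. The bias in the expected placebo rate is (risk difference)/75 per such subject, with a ceiling of 1.3 points.

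This rests on three assumptions: that throughout means every dose, since neither document defines it; that the arms are of planned size; and that partial exposure carries the full evolocumab risk. If no subject had mixed exposure, nothing changes. The case for acting is that the rule is cheap to set in advance and awkward to choose after unblinding, if such a subject then appears.

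**What to change.** Before unblinding, amend SAP 5.3, which SAP 6.2 already refers to, so that for safety and antibody analyses:

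1. The actual treatment group is evolocumab if the subject received at least one evolocumab dose, and placebo otherwise.
2. A mixed-exposure subject stays in the randomized dose-frequency comparison (Q2W or QM) unless the other frequency was received throughout.
3. All mixed-exposure subjects are listed with product and date of each dose and the onset date of each event.
4. SAP section 10 records this as a departure from Protocol 10.1.2 and the synopsis.

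Efficacy grouping is unchanged.

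The cost is a revised definition, an entry in SAP section 10 and one listing. No new data are needed: "The box number of investigational product (active drug or placebo) is to be recorded on each subject's Drug Administration electronic case report form". The rule must be written while blinded and applied once box contents are known. The downside is that events before the first evolocumab dose in such a subject are counted under evolocumab; the dates in the listing make these visible.

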10.1.3 Covariates and Sub-groups

Baseline covariates and sub-groups include, but are not limited to:

- Stratification factors:
 - entry CV risk (high/very high CV risk vs not high/very high CV risk).
- Age: < 65 year, ≥ 65 years
- Sex

- Medical history of Diabetes (yes/no)
- Study baseline LDL-C: < median / \geq median
- Family history of premature coronary heart disease (yes/no)
- Baseline PCSK9
- Diagnosis of HeFH according to protocol defined criteria

Missing data will not be imputed for safety endpoints.

10.2 Sample Size Considerations

The sample size for this study has been considered to meet the requirement from regulatory authority (Drug Registration Regulation No 28; Oct 2007).

The planned total sample size is 450 subjects (150 randomized to evolocumab SC 140 mg Q2W, 150 randomized to evolocumab SC 420 mg QM, 75 randomized to placebo Q2W and 75 randomized to placebo QM). The primary analysis will require the tests of each co-primary endpoint to be significant at level of 0.05. The sample size should provide adequate power to determine the superiority of evolocumab (either Q2W or QM) relative to respective placebo (Q2W or QM) as measured by the co-primary endpoints.

From the phase 3 study 20120122 and phase 2 study 20110155, the mean treatment effect of evolocumab 140 mg Q2W and 420 mg QM compared to placebo in percent change from baseline in LDL-C at week 12 was at least -50.3%, with the smallest treatment effect of -44.6% estimated from 95% confidence intervals. For the co-primary endpoint of mean percent change from baseline in LDL-C at weeks 10 and 12, the mean treatment effect of evolocumab 140 mg Q2W and 420 mg QM compared to placebo was at least -62.4%, with the smallest treatment effect of -57.2% estimated from 95% confidence intervals.

The assumed treatment effect of evolocumab in LDL-C reduction is 40%, with a common SD of 25%. As the co-primary endpoints are correlated, the planned sample size will provide approximately at least 98% (99% \times 99%) power in testing the superiority of each evolocumab dosing regimen over placebo on the co-primary endpoints, assuming a 10% drop out rate.

Since the testing statistics from Q2W and QM groups are independent, there is a 96% chance (98% \times 98%) to show the superiority of both evolocumab dosing regimens over placebo.

The power calculation is derived using SAS Enterprise Guide version 6.1.

10.3 Access to Individual Subject Treatment Assignments by Amgen or Designees

Blinded individuals will not have access to unblinded information until the study is formally unblinded. Unblinding and potentially unblinding information should not be distributed to the study team, investigators or subjects prior to the study being formally unblinded (eg, the formal unblinding may occur at the final analysis rather than during the primary analysis) except as specified (eg, [Section 5.2](#) and [Section 9.2.2.2](#)).

Amgen staff members who are involved in randomization, biological sample management, performing PK, and anti-evolocumab assay analysis will have treatment assignment information, but will not have access to subject level data from the clinical trial database.

10.4 Planned Analyses

10.4.1 Primary Analysis

The primary analysis will be performed when all subjects have either completed all scheduled study visits or have early terminated from the study. At that time, the database will be cleaned, processed and locked; the study will also be unblinded.

10.5 Planned Methods of Analysis

10.5.1 General Considerations

Efficacy and safety analyses will be performed on the FAS. Unless specified otherwise, the FAS will be the default analysis set in this study and data will be summarized by randomized treatment group. Analyses will be performed separately by each dose frequency (Q2W and QM) unless specified otherwise. The superiority of evolocumab to placebo will be assessed for all efficacy endpoints.

Subject disposition, demographics, baseline characteristics, and exposure to investigational product will be summarized.

[figure not shown]
Summary statistics for continuous variables will include the number of subjects, mean, median, standard deviation, or standard error, minimum, and maximum. For categorical variables, the frequency and percentage will be given.

Missing data will not be imputed for safety endpoints.

Multiplicity Adjustment Method

The analyses of Q2W and QM will be performed as 2 independent experiments. In order to preserve the familywise error rate at 0.05 within each independent experiment (Q2W and QM), methods of adjusting for multiplicity due to multiple endpoints

(co-primary and secondary efficacy endpoints) within each dose frequency are described in the diagram below.

Testing of each endpoint pair will result in a single p-value, and for secondary endpoints these p-values will then be used in the Hochberg procedure. The following method will be used to preserve the family wise error rate for the co-primary and secondary endpoints for testing within each dose frequency:

1. If the treatment effect from the primary analysis of the co-primary endpoints are both significant at a significance level of 0.05, statistical testing of the tier 1 secondary efficacy endpoints (as defined in [Section 10.5.3](#)) will follow the Hochberg procedure at a significance level of 0.005 ([Hochberg, 1988](#))
2. If all tier 1 secondary efficacy endpoints are significant, the tier 2 secondary efficacy endpoints will be tested using the Hochberg procedure at a significance level of 0.05.
3. If not all tier 1 secondary efficacy endpoints are significant, the tier 2 secondary efficacy endpoints will be tested using the Hochberg procedure at a significance level of 0.045 ([Wiens, 2003](#))

Unless specified otherwise, all other hypothesis testing will be 2-sided with a significance level of 0.05.

